## 10.5 STATISTICAL ANALYSES AND METHODS

All safety, effectiveness and exploratory data will be summarized. Continuous data will be summarized using descriptive statistics including means, standard deviations, medians, lower and upper quartiles, and ranges. Categorical variables will be summarized with frequencies and percentages. Confidence intervals will be calculated for key parameters or estimates as warranted.

A complete description of the statistical analyses and methods will be available in a statistical analysis plan (SAP), which will be finalized before the database is locked.

### 10.5.1 Safety Analyses

Adverse events will be monitored throughout each core study and the open label extension. Adverse events will be considered to be treatment emergent (TEAE) if they begin between the first day of treatment with ZX008 and the last day of the Post-dosing period or occur prior to first ZX008 treatment but increase in severity after ZX008 treatment begins.

The number and percentage of subjects in each treatment group with TEAEs will be displayed by body system and preferred term using the Medical Dictionary for Regulatory Activities (MedDRA). A table will enumerate the TEAEs that occur in at least 5% of subjects. A separate summary will be provided for all serious AEs (SAEs). Selected summaries will be repeated broken out by age group, ie, for ages < 6 years and  $\geq$  6 years.

Hematology and chemistry laboratory results will be summarized using shift tables that tabulate the proportion of subjects who have lab results that change from pre-ZX008 baseline, where pre-ZX008 baseline values will be determined from lab results obtained prior to first treatment with ZX008. The shift tables will be presented for each time point where lab results are collected. Mean change from pre-ZX008 baseline will also be calculated for continuous hematology and chemistry results at all time points available.

Physical examinations, vital signs, ECG, ECHO and body weight will be summarized appropriately. All safety summaries will be based on the SAF Population.

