**Duration of Treatment:**

All subjects will receive ZX008 for up to approximately 36 months. All subjects, including those who prematurely discontinue from the study, will undergo an up to 2-week taper of study medication, at the conclusion of the study.

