- f: For subjects enrolling from one of the core studies, use core study Visit 12 information unless complete neurological examination is warranted based on significant changes in subject status.
- g: ECHOs will be performed at Months 1, 3, 6, 9, 12, 15, 18, 21, 24, 27, 30, and 33.
- h: The Months 3, 6, 9, 12, 15, 18, 21, 24, 27, 30, and 33 ECHO may be performed any time within 3 weeks prior to the study visit. If a subject discontinues early from the study, the ECHO should be scheduled as soon as practical (see Table 7).
- i: Females of child-bearing potential
- j: For subjects enrolling from one of the core studies, use data collected at Visit 12 of ZX008-1501 or ZX008-1502 for Visit 1 unless clinical laboratory evaluation is warranted based on significant changes in subject status. Visit 2 clinical laboratory evaluation is optional based on subject status for all cohorts.
- k: Visits 6, 15, and 27 only.
- l: Visits 3 and 4 (Months 1 and 2) only.
- m: Only adverse events related to cardiac safety will be collected at this visit (see Table 7).
- n: Not to be completed for de novo subjects >18 years old.
- o: For subjects who are entering the separate extension trial or who transition to commercially available drug, post-dosing and cardiac safety follow-up visits are not required in this trial.

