If after approximately the midway point of the first 30 days on ZX008 0.2 mg/kg/day there is a clinically meaningful worsening in seizure type, frequency, and/or duration compared with the recent treatment in the core study, the investigator, in consultation with the Medical Monitor, may increase the dose to 0.4 mg/kg/day (maximum 30 mg/day for subjects who are not receiving concomitant STP; 20 mg/day for subjects who are receiving concomitant STP). A clinically meaningful worsening would be an increase in frequency, severity or duration of existing seizures, or emergence of a new seizure type. The description of the clinical worsening must be documented in the source notes and case report form (CRF). Further increase to 0.8 mg/kg/day (maximum 30 mg/day for subjects who are not receiving concomitant STP and to 0.5 mg/kg/day (maximum 20 mg/day) for subjects who are receiving concomitant STP) could also be undertaken for the same conditions after a minimum of 4 days on 0.4 mg/kg/day, if the condition has not stabilized on the 0.4 mg/kg/day dose. Dosing outside of the specified range (ie, 0.2 to 0.8 mg/kg/day or 0.5 mg/kg/day for subjects who are receiving concomitant STP) may be considered after consultation between the investigator and Medical Monitor.

A follow-up ECG and ECHO will be performed 3 and 6 months after study drug discontinuation for early termination and for those subjects who complete the study.

Caregivers will use a diary daily to record the number/type of seizures, dosing, and use of rescue medication. A schedule of assessments is provided in [Table 1](#) and [Table 2](#).

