## 6.2 POST-DOSE VISIT (CLINIC VISIT 17; STUDY DAY 1099)

If the subject completes the study (or discontinues from the study early), and is not transitioning to another extension protocol or switching to commercially available drug, the subject will visit the clinic on Study Day 1099 (or 14 days after the day of discontinuation)

The following procedures will be performed:

- Record AEs
- Record AESI
- Record concomitant medications

- Collect used, partially used and unused study medication; perform drug accountability and review with parent/caregiver

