**Table 8. Schedule of Post-Treatment Cardiac Follow-up**

Parameter	Duration of Fenfluramine Treatment				Have had any cardiac sign or symptom regardless of the time on study drug a
	Less than 2 weeks Cumulative	2 to 4 weeks	> 4 and < 13 weeks	> 13 weeks	
ECHO	No	Yes, 3 months post-treatment	Yes, 3 months post-treatment	Yes, 3 and 6 months post-treatment	Yes, 3 and 6 months post-treatment, and until resolved, or stable and unlikely to change
ECG	No	Yes, 3 months post-treatment	Yes, 3 months post-treatment	Yes, 3 and 6 months post-treatment	Yes, 3 and 6 months post-treatment and until resolved, or stable and unlikely to change
Physical examination	No	Yes, 3 months post-treatment	Yes, 3 months post-treatment	Yes, 3 months post-treatment only	Yes, 3 and 6 months post-treatment, and until resolved, or stable and unlikely to change

a Positive sign or symptom includes any development of valve thickening or regurgitation (“trace” or greater in mitral, aortic; mild or greater in pulmonary, tricuspid), or sign or symptom indicative of potential pulmonary hypertension as adjudicated by the IPCAB.

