### 8.4 OBSERVATION PERIOD FOR ADVERSE EVENT REPORTING

The observation period for AE and SAE reporting for de novo subjects will start at the time of giving written informed consent for participation in the current study and finish 15 days after the last dose of study drug or the last visit, whichever is later. For subjects who participated in one of the core studies, the observation period for adverse events will start at Visit 1 of 1503 and finish 15 days after the last dose of study drug or the last visit, whichever is later. Ongoing AEs from the core studies will be considered medical history unless there is an increase in the frequency or severity of the condition from the core study.

If the investigator becomes aware of an SAE that has started after the observation period has finished, and the event could in some way be associated with IMP (irrespective of whether or not it is considered by the investigator to be causally related to IMP), then this must also be reported to the Sponsor (see Section 8.6).

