#### Post-dosing Period

The Post-dosing Period begins immediately at the end of OLE Treatment Period and extends for 2 weeks.

After at least 1 year of treatment in Study 1503 subjects who participated in one of the core studies will transition to a separate extension study (Study 1900) once that study is approved and the study site is initiated. Continuation in a separate extension protocol will be based on benefit/risk and continued eligibility criteria being met. De novo subjects must have participated in this trial for at least 3 months with at least 1 ECHO completed and continue to meet eligibility requirements to be eligible to transition to a separate extension protocol. Alternatively, subjects will transition to commercial product once it is available if they have had an ECHO within 3-6 months before starting commercial drug. For subjects who are entering the separate extension trial or who transition to commercially available drug, post-dosing and cardiac safety follow-up visits are not required in this trial. Subjects who transition to commercially available drug will have follow-up ECHOs within the required timeframe while on commercial drug.

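### The treatment-emergent window closes 2 weeks after OLE treatment ends, so non-serious cardiac AEs with onset at the 3- and 6-month follow-up visits are collected but left out of the TEAE incidence tables

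*Protocol*

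**What the plan says.** Section 10.5.1 makes an AE treatment emergent "if they begin between the first day of treatment with ZX008 and the last day of the Post-dosing period". The only other route is for an event that was present before first ZX008 and became more severe afterwards. Section 10.4 fixes the closing date: "The Post-dosing Period begins immediately at the end of OLE Treatment Period and extends for 2 weeks". Section 6.2 places the post-dose visit at Study Day 1099.

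Collection runs longer. Under Section 8.4 the AE and SAE observation period will "finish 15 days after the last dose of study drug or the last visit, whichever is later". Section 3.1 states that "A follow-up ECG and ECHO will be performed 3 and 6 months after study drug discontinuation". For more than 13 weeks of treatment, Table 8 gives the ECHO and ECG entries as "Yes, 3 and 6 months post-treatment". Footnote m of Table 1 says of Visits 18 and 19: "Only adverse events related to cardiac safety will be collected at this visit"; footnote l of Table 2 says the same for subjects from Study 1504.

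Dosing does not stop when OLE treatment ends. According to the synopsis (Duration of Treatment), subjects "will undergo an up to 2-week taper of study medication". The dosing steps filled in within Tables 5 and 6 end by Day 8.

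**The concern.** The counting rule and the collection rule do not meet. The schedule sends subjects who stop the drug back twice for ECHO and ECG and records cardiac AEs there, but the definition behind the AE incidence tables has closed months earlier.

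The primary objective is long-term safety and tolerability (Section 2.1), and Section 1.2 names heart valve disease and pulmonary hypertension as the reason fenfluramine left the US market. Section 1.3 reports the study's own cardiac experience to date as TEAEs of abnormal echocardiogram. The TEAE count is therefore the figure readers will look at, and it would omit new non-serious cardiac AEs arising in off-drug follow-up. Section 8.8 expects that such events can be non-serious: it requires pulmonary hypertension, and valvulopathy found outside study monitoring, to be reported even when no SAE criterion is met.

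The starting point raises a second, smaller issue. Because the 2 weeks begin at the end of OLE treatment, the taper is spent inside them, and the off-drug time that remains is shorter than the 15 days in Section 8.4.

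**Working it through.** **Inputs.** End of OLE treatment for a completer: Day 1085 (Table 1). Post-dosing Period: 14 days (Section 10.4). Cardiac visits: 3 and 6 months after the last dose, window +30 days (Table 7). Taper: 0, 4 or 8 days by current dose (Tables 5 and 6), or up to 14 days (synopsis). Assumption: one month = 30.44 days, so 3 months = 91.3 days and 6 months = 182.6 days.

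**The plan's own figures.** 1085 + 14 = 1099, the post-dose visit day in Section 6.2. 156 + 2 = 158 weeks, the duration in Section 3.3. Both reproduce.

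**Formulas.** Last dose L = 1085 + taper. Off-drug days inside the TEAE window = 1099 - L. Gap to a cardiac visit = L + 91.3 (or 182.6) - 1099. Shortfall against the 15-day limb of Section 8.4 = (L + 15) - 1099.

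| Taper (days) | Last dose (Day) | Off-drug days in window | Shortfall against 15 days | 3-month visit: days after cut-off | 6-month visit: days after cut-off |
|---|---|---|---|---|---|
| 0 | 1085 | 14 | 1 | 77 | 169 |
| 4 | 1089 | 10 | 5 | 81 | 173 |
| 8 | 1093 | 6 | 9 | 85 | 177 |
| 14 | 1099 | 0 | 15 | 91 | 183 |

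Using the +30-day visit window in full moves the two gaps to at most 121 and 213 days. If an early terminator's OLE treatment is taken to end on the day of discontinuation, the same differences apply, because everything is measured from that day.

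**Does any off-drug ECHO fall inside the window?** The end-of-study ECHO is due between Days 1064 and 1085 (Section 6.1.5). The post-dose visit lists AEs, AESIs, concomitant medication and drug accountability, but no ECHO (Section 6.2). So both scheduled post-treatment ECHOs, 2 of 2, come after the cut-off.

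**Where does a cardiac AE with onset at Visit 18 or 19 go?**
- TEAE tables by body system and preferred term, and the table of TEAEs in at least 5% of subjects: no.
- SAE summary: yes if serious, since Section 10.5.1 describes it as covering all SAEs.
- ECHO and ECG summary: the measurement may appear. The section names no time points for it, although it does so for laboratory results.
- AESI: not clearly. Section 7.3.8 says the ECHO thresholds are in Table 10, but Table 10 lists only metabolic/endocrine and neuropsychiatric items.

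A non-serious cardiac AE of this kind therefore enters no AE incidence table that the protocol describes.

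**The case against.** A reader might infer that valvulopathy or pulmonary hypertension first found at follow-up is excluded from the primary safety analysis, or collected and then lost. The documents do not support that. No analysis carries that name. ECHO and ECG are safety endpoints in their own right (Section 2.4.2), and Section 10.5.1 plans to summarize them on the Safety Population without a closing date. Section 10.5 says that all safety data will be summarized. Serious cases reach the SAE summary.

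Three further limits stand. TEAE status follows onset, not detection, so a finding that began on drug and is still followed at Visit 18 remains a TEAE. Subjects who enter the extension study or move to commercial drug have no cardiac follow-up here (Section 3.1), so only those who stop ZX008 are affected. Central reading, IPCAB adjudication and case-by-case IDSMC review (Sections 3.7.2, 8.9.1 and 4.4) deal with late cardiac findings whatever the tables show.

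It can also be said that a post-treatment cardiac table is ordinary SAP content, and the SAP is not shown. That is true of an extra table, and its absence alone would be no finding. It does not settle the definition: the protocol states a specific closing date, and a SAP that kept it would keep the gap. These points narrow the concern but leave the mismatch between Section 10.5.1 and Section 8.4 with its footnotes.

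**Conclusion.** The point holds as a mismatch between what is collected and what is counted. In subjects who stop ZX008 without moving to the extension or commercial drug, non-serious cardiac AEs with onset after the Post-dosing Period are left out of the TEAE incidence tables. The follow-up visits lie about 77-91 and 169-183 days beyond the cut-off. Separately, the window holds 6 off-drug days after an 8-day taper and none after a full 2-week taper, against the 15 days of Section 8.4.

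This rests on onset being recorded at or near the follow-up visit and on the month length stated above. The number of events affected cannot be worked out from the protocol. A zero count for late cardiac harm does not follow, because the SAE and ECHO summaries remain open to it.

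**What to change.** In Section 10.5.1, do one of two things for cardiac events:
- count cardiac AEs from first ZX008 through the last cardiac follow-up visit, with a flag for post-treatment onset; or
- keep the present cut-off and add a separate table of post-treatment cardiac AEs and follow-up ECHO findings.

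For other AEs, run the window from the last dose including taper and reconcile it with Section 8.4. That section should also say what its last-visit limb means for non-cardiac AEs, since the footnotes restrict Visits 18 and 19 to cardiac events. The taper length in the synopsis and in Tables 5 and 6 should be reconciled too, because the off-drug part of the window depends on it.

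The cost is one definition or one table, with no new data collection. A few more off-drug events will be counted; the flag or the separate table keeps them distinguishable from on-treatment events.

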### **1.9 RATIONALE FOR INCLUDING DE NOVO SUBJECTS**

Subjects who are >18 to ≤35 years of age at the time of screening, and who meet all other eligibility criteria may be eligible for participation after discussion with the Medical Monitor and sponsor about the potential risks and benefits for receiving ZX008. Participation for these subjects will be at the discretion of the sponsor.

Epileptic seizures tend to become less frequent and less severe after childhood; however, the mortality rate remains high. One study on the long-term outcome of 24 adult patients with DS reported 5 (20.8%) deaths, at a mean age of 24.8 years, one by status epilepticus, three by sudden unexpected death in epilepsy (SUDEP), and one of unknown cause ([Genton 2011](#)).

Fever sensitivity (temperature variations) persists throughout the clinical course of DS, but its impact on seizure frequency and severity is milder than in infancy. Generalized convulsive seizures, mostly reported as generalized tonic-clonic seizures persist, often with a focal onset but are less frequent than in childhood and mostly nocturnal. Some of these major convulsive seizures have less typical aspects, for example, bilateral or asymmetric tonic posturing, followed in some cases by a tonic vibratory state or clonic movements ([Oguni 2001](#);

Akiyama 2010). Other seizures like myoclonic seizures, atypical absences, and complex partial seizures are less common in adulthood. Motor abnormalities are also common in adulthood, as is intellectual disability. Dependency in adulthood is nearly constant.

Including subjects >18 to ≤35 years of age provides the opportunity to investigate the impact of ZX008 on DS outcomes as subjects transition to adulthood.

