It is acknowledged that the initial dose of ZX008 in this study, 0.2 mg/kg/day, may or may not be effective or may be less effective than 0.8 mg/kg/day (or 0.5 mg/kg/day for subjects taking concomitant STP) for some subjects and some subjects may experience a worsening of their seizure condition after transitioning to the lower dose. However, there is benefit in identifying a minimally effective dose for all subjects in the study since the cardiotoxicity of fenfluramine appears to be dose-related in adults. The dosing instructions of this protocol permit dose adjustment during the first month of fixed dosing at 0.2 mg/kg/day if a clinically meaningful worsening occurs, such as an increase in frequency, severity or duration of existing seizures, or emergence of a new seizure type.

The approximate volume of blood (240 mL) planned for collection from each subject over the course of the entire study (approximately 3 years, but not including repeat or additional tests ordered by the investigator) presents no undue risk to the subjects.

The ZX008 0.2 mg/kg/day, 0.4 mg/kg/day, 0.6 mg/kg/day, 0.8 mg/kg/day, and 0.5 mg/kg/day (in subjects taking concomitant STP) doses are believed to be therapeutic doses, which could provide sufficient anti-epileptic support for a sustained period of time during the study.

The available information suggests that the present clinical study has an acceptable risk-benefit ratio.

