### **3.2 NUMBER OF SUBJECTS**

Up to approximately 340 subjects from the core studies and up to 50 subjects who did not participate in the core studies may be enrolled.

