### 4.1 INCLUSION CRITERIA

Subjects meeting all of the following inclusion criteria may be enrolled into the study:

1. Subject is aged 2 to 18 years inclusive, as of the day of the core study Screening Visit.
2. Subject has satisfactorily completed the core study in the opinion of the investigator and the Sponsor.

NOTE: Those subjects who do not complete the 12-week Maintenance Period of the core study may, on a case-by-case basis, be eligible for entrance after consideration of the circumstances of the early termination and the potential benefit-risk of continued participation in a ZX008 trial. The decision whether to permit open-label extension study participation resides solely with the Sponsor, who may consult with the site investigator, the IPCAB and/or the IDSMC.

3. Subject is male or non-pregnant, non-lactating female. Female subjects of childbearing potential must not be pregnant or breast-feeding. Female subjects of childbearing potential must have a negative urine pregnancy test. Subjects of childbearing or child-fathering potential must be willing to use medically acceptable forms of birth control, which includes abstinence, while being treated on this study and for 90 days after the last dose of study drug.
4. Subject has documented medical history to support a clinical diagnosis of DS, where convulsive seizures are not completely controlled by current antiepileptic drugs.
5. Subject has been informed of the nature of the study and informed consent has been obtained from the legally responsible parent/guardian.
6. Subject has provided assent in accordance with IRB/IEC requirements, if capable.
7. Subject's caregiver is willing and able to be compliant with diary completion, visit schedule and study drug accountability.
8. Subject's parent/caregiver has been compliant with diary completion during the core study, in the opinion of the investigator (eg, at least 90% compliant).
9. Subjects entering from study ZX008-1504 must be receiving a therapeutically relevant and stable dose of CLB and/or VPA, and STP (Cohort 1 dose regimen 3 and Cohort 2 only) for at least 4 weeks prior to screening and are expected to remain stable throughout the study.
10. Subjects who are >18 to ≤35 years of age at the time of screening and did not participate in one of the core studies must meet criteria 3 to 7 above and the following criteria below in order to be considered for participation. Participation is at the discretion of the Sponsor:

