## **10. STATISTICS**

### **10.1 DETERMINATION OF SAMPLE SIZE**

The sample size will be determined by the number of subjects who participate in 1 of 3 core studies (Study ZX008-1501, Study ZX008-1502, or Study ZX008-1504) and who volunteer for the extension study and meet the necessary criteria for enrollment. Approximately 100-120 subjects are expected to participate in each of the core studies; thus, if all participants also enroll in the extension, the total sample size of the extension study would be approximately 340.

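### The one age split fixed for adverse-event summaries (<6 vs ≥6 years) pools the de novo adults with children from 6, so no stated safety summary gives an adult rate

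*Protocol*

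**What the plan says.** Section 10.5.1, in its adverse-event paragraph, fixes one age breakout: "Selected summaries will be repeated broken out by age group, ie, for ages < 6 years" and, as the second group, 6 years and above. The wording defines the grouping; it does not offer it as an example. The same paragraph plans a full TEAE table by body system and preferred term, a table of TEAEs reaching 5% of subjects, and a separate SAE summary. ECG, ECHO and body weight are to be summarised in a suitable way, with no age split named. Section 10.3 treats all subjects as a single treatment group.

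On who is enrolled, section 3.2 gives "Up to approximately 340 subjects from the core studies and up to 50 subjects who did not participate in the core studies". Core subjects meet inclusion criterion 1 in section 4.1: "Subject is aged 2 to 18 years inclusive, as of the day of the core study Screening Visit". De novo subjects come in under criterion 10: "Subjects who are >18 to ≤35 years of age at the time of screening and did not participate in one of the core studies". Section 1.9 says that including them "provides the opportunity to investigate the impact of ZX008 on DS outcomes as subjects transition to adulthood". Section 10.5.2.1 limits the change-from-baseline effectiveness analyses to subjects from Studies 1501, 1502 and 1504 Cohort 2. The synopsis likewise excludes de novo subjects from effectiveness analyses, while adding that change over time will be described.

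**The concern.** Long-term safety is the primary objective, and adults were admitted deliberately. The protocol handles them differently at entry: criterion 10.h makes mild or greater mitral or aortic regurgitation exclusionary for subjects over 18. Section 1.10 also notes that "the cardiotoxicity of fenfluramine appears to be dose-related in adults". With adults outside the change-from-baseline analyses, the safety tables are where most of the planned information about them would lie. The upper age group, however, runs from 6 to 35 years, and children are likely to dominate it. If an adverse event is more frequent in adults than in children, the displayed rate will understate the adult rate, and the reader cannot recover that rate from the stated summaries.

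**Working it through.** **The plan's own figure.** Section 10.1 says "Approximately 100-120 subjects are expected to participate in each of the core studies" and arrives at about 340 across three studies. Three times 100, 110 and 120 is 300, 330 and 360, so 340 lies inside the range. Section 10.1 does not mention the de novo subjects; section 3.2 adds up to 50, for a maximum of 340 + 50 = 390.

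**Inputs.** Core subjects N = 340 and de novo adults A = 50 (section 3.2). The share f of core subjects aged 6 or older is not stated, so it is an assumption and is varied.

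**Event confined to adults.** Dilution in the ≥6 column is the adult rate divided by the displayed rate, (f × N + A) / A.

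| f (assumed) | Size of ≥6 group | Adults' share | Dilution |
|---|---|---|---|
| 44% | 200 | 25% | 4.0 |
| 50% | 220 | 23% | 4.4 |
| 76% (ages 2-18 evenly spread, 13 of 17 years) | 310 | 16% | 6.2 |
| 100% | 390 | 13% | 7.8 |

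If only 25 adults enrol, the result is (170 + 25)/25 = 7.8 at f = 50% and (340 + 25)/25 = 14.6 at f = 100%.

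**Event also seen in children.** Take assumed rates of 10% in adults and 1% in children aged 6-18, with f = 76% (260 children). The displayed rate is (0.10 × 50 + 0.01 × 260)/310 = 7.6/310 = 2.45%, and 10/2.45 is about 4.1-fold. With 25 adults and the same rates it is (2.5 + 2.6)/285 = 1.8%.

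**The 5% table.** It covers all subjects. With 390 subjects the cut-off is 0.05 × 390 = 19.5, so an adult-only event needs 20 cases, or 40% of 50 adults, to be listed there.

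**With a separate adult column.** The dilution disappears. With 50 adults, the chance of at least one case is 1 − (1 − p)^50: 64%, 92% and 99.5% for a true risk p of 2%, 5% and 10%. Zero cases in 50 gives a one-sided 95% upper bound of 1 − 0.05^(1/50) = 5.8%.

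**The case against.** The strongest reply is that the detail belongs to the SAP. Section 10.5 leaves the complete description to that document, which is not at hand. It may add an adult or de novo column, and section 10.5.1 does not say that no other subgroup will be shown. That is fair, and the point is therefore not that an analysis is missing. It is that the grouping the protocol does fix does not suit the population it now enrols, and a SAP that followed it literally would carry the problem over.

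Several stronger readings are tempting, but the documents do not support them:

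- A reader might infer that an adult harm could go unseen, or would vanish because it falls below 5%. The full TEAE table and the SAE summary have no frequency cut-off, and the 5% table is an additional listing over all subjects, not a threshold applied within the ≥6 column.
- A reader might infer that the split dilutes the ECHO findings. It is written for adverse-event summaries, and no split of any kind is fixed for ECHO. ECHOs are centrally read and escalated case by case (sections 3.7.2 and 8.9.1), and the IDSMC reviews valve disease and pulmonary hypertension as they occur (section 4.4).
- Table 12 has separate rows for mild findings at ≤18 and >18 years, but the levels in those rows are identical, so it lends little weight. Section 1.10 speaks of dose dependence in adults, not of greater susceptibility with age.
- A single fourfold figure might be quoted. It holds only for particular assumed rates and age mixes.

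**Conclusion.** The point holds in a limited form. The only age breakout stated for safety was not adapted to the de novo adults, so they are pooled with children from 6 years and no stated safety summary yields an adult rate. For an adult-only event the dilution is about 4.4- to 7.8-fold, assuming 340 core subjects, all 50 adult places filled and 50-100% of core subjects aged 6 or older. It is larger with fewer adults, and smaller if fewer core subjects are in that age range or if children share the risk (about 4-fold for 10% against 1% with 76% aged 6 or older). What is obscured is the adult-specific rate, not the existence of adult cases. Trial conduct and hypothesis tests are unaffected; what suffers is how well the primary objective can be read for a group enrolled on purpose.

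**What to change.** In section 10.5.1, replace the two-way split with <6, 6-18 and >18 years by age at OLE entry, for the selected TEAE and SAE summaries. List events in the >18 column without the 5% cut-off. Use the same three groups for the ECHO and body-weight summaries, where no split is now fixed. Core subjects who have passed 18 by OLE entry would join the adult column; their number is not given.

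The cost is one more column in tables already planned, with no new data or visits. Estimates from at most about 50 adults will be imprecise (the 5.8% bound for zero events shows how much), so they should carry confidence intervals.
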